9.11 Study Termination

The Sponsor may terminate the study as a whole or at individual study sites under the following circumstances:

- Suspicion of risk to subjects, including occurrence of high rate of known AEs or unexpectedly high rate of unexpected AEs
- Poor site compliance with the study protocol
- Inadequate site enrollment
- Obtaining new scientific knowledge that shows that the study is no longer valid or necessary
- Persistent non-compliance with IRB or regulatory requirements
- Persistent failure to comply with obligations arising from the clinical trial agreement
- Other business reasons (e.g., insolvencies or business entity liquidation)

The Sponsor will document reasons for study suspension and notify relevant site Investigators and governing IRBs. If suspension occurred because of a safety issue, all Investigators will be notified. When terminating the study, the Sponsor and Investigator will assure that adequate consideration is given to the protection of the subjects' interests.

9.12 Study-Related Assessments

9.12.1 Knee Injury and Osteoarthritis Outcomes Score (KOOS JR.)

The KOOS JR. score consists of 7 questions from 3 subscales: Stiffness (1 question), Pain (4 questions), and Function in daily living (2 questions). Standardized answer options are given (5 Likert boxes) and each question is assigned a score from None (0) to Extreme (4). A normalized score (100 indicating no symptoms and 0 indicating extreme symptoms) is calculated. A copy of the KOOS JR. is located in Attachment 1. Completion of the KOOS JR. questionnaire will take approximately 5 minutes to complete. After completion by the Subject, the study coordinator or designee will enter into the CRF.

9.12.2 Numeric Rating Scale for Pain (NRS for Pain)

The Numeric Rating Scale for Pain (NRS for Pain) is a measure of pain intensity. The investigator or designee conducts the 11-point scale verbally with the research subject in reference to the target knee. The investigator or designee will ask the following questions,

[figure not shown]
- “On a scale of 0 to 10, with 0 being no pain at all and 10 being the worst pain imaginable, how would you rate your pain IN THE PAST 7 DAYS when standing from a seated position?”
- “On a scale of 0 to 10, with 0 being no pain at all and 10 being the worst pain imaginable, how would you rate your pain RIGHT NOW when standing from a seated position?”

The Subject responds verbally and the study coordinator or designee will record the response.

The NRS for Pain will be completed by the Subject and will take approximately 2 minutes to complete. The study coordinator or designee will enter the data into the CRF.

9.12.3 Subject Satisfaction Questions

Subject satisfaction questions will be verbally administered by the study coordinator or designee at Visit 6 and Visit 7. Questions will take approximately 3 minutes to complete. The Subject satisfaction questions are located in Attachment 2.

10. STATISTICAL METHODS

10.1 Introduction

This is a prospective, randomized, single-site, post-market trial to evaluate the iovera[°] device in treating pain associated with total knee arthroplasty (TKA). The study is designed to investigate whether iovera[°] treatment prior to TKA decreases cumulative patient opioid use over the course of 6 weeks following TKA while maintaining similar levels of pain and functioning as measured by reductions from the Baseline visit in the KOOS JR. score.

The study will also investigate whether there is a treatment effect of iovera[°] on the following measures of effectiveness: NRS for Pain, Timed Get Up and Go Test, [REDACTED]

One study site within the United States will screen a sufficient number of subjects to ensure that 120 subjects (randomized 1:1 to obtain approximately 60 iovera[°] subjects and 60 Standard of Care subjects) will be randomized.

10.2 General

Categorical data will be summarized using frequency tables, presenting subject counts and percentages. Continuous variables will be summarized using descriptive statistics (number of subjects, mean, standard deviation, median, minimum, and maximum).

The SAS system will be used to perform all statistical analyses.

Exact binomial confidence intervals will be generated for proportions. Confidence intervals based on the t-distribution will be generated for means and differences of means. Fixed sequential testing will be performed to control the overall Type I error rate.

Except where noted otherwise, within-subject change-from-baseline (pre-treatment baseline) values for a variable are calculated as:

$$\text{Change-from-Baseline} = \text{Follow-Up value} - \text{Pre-Treatment value},$$

such that a positive value indicates an increase from the pre-treatment value to the follow-up value, whereas a negative value indicates a decrease.

10.3 Analysis Populations

10.3.1 Screening Population

All subjects who are screened for the study will be included in the Screening Population. For this population, only an accounting of the numbers of subjects screened in the study, plus the reasons given for subjects not being enrolled in the study, will be summarized.

10.3.2 ITT (Intent to Treat) Population

All subjects who are randomized will be included in the ITT Population. Subjects will be analyzed according to the treatment group to which they were randomized. The primary analyses of effectiveness will be conducted based on the ITT Population.

10.3.3 Per-Protocol Population

The Per-Protocol Population is defined as the group of subjects who are randomized, who receive the treatment to which they were randomly assigned, and who complete their 6-week visit without any major protocol deviations. Subjects will be analyzed according to the treatment group to which they were randomized. Secondary analyses of effectiveness will be conducted based on the Per-Protocol Population.

10.3.4 Safety Population

All subjects who receive study treatment will be included in the Safety Population. Subjects will be analyzed according to the treatment they actually receive, regardless of their randomized treatment. All safety analyses will be based on the Safety Population.

10.4 Study Endpoints

10.4.1 Primary Effectiveness Endpoint

The primary effectiveness endpoint is the cumulative consumption of opioids from the time of hospital discharge to 6 weeks post-TKA Surgery. Opioid consumption will be converted to morphine equivalents, and subject consumption will be verified by pill count at follow-up visits. The cumulative morphine equivalent will be divided by the number of days to provide the Total Daily Morphine Equivalent (TME) for the subject.

The difference in the mean TME between the two treatment groups will be calculated as Standard of Care TME mean – Active TME mean, such that a positive difference indicates that the Standard of Care Treatment group had a larger mean TME than the Active Treatment group, while a negative difference indicates the opposite. A positive difference between the two treatment groups reflects a positive outcome for the study.

Let $\mu_{1,Active}$ and $\mu_{1,SOC}$ denote the true mean TMEs for the active and standard of care treatments, respectively. Then the null and alternative hypotheses for the primary effectiveness endpoint are as follows:

$$H_0: \mu_{1,Active} \geq \mu_{1,SOC}$$

$$H_1: \mu_{1,Active} < \mu_{1,SOC}$$

A one-sided, two-independent sample, Satterthwaite t-test will be used to test the null hypothesis. The Primary Effectiveness Study Objective will be met if this t-test is statistically significant using a one-sided $\alpha = 0.025$ level of statistical significance.

This endpoint will be summarized by treatment group using descriptive statistics. The difference in mean TMEs between the two treatment groups and a 95% confidence interval based on the t-distribution for the true difference in the mean TMEs between the two treatments will also be provided.

The database will be “soft-locked” after all 6 week data has been collected (all data monitored with the exception of data points collected beyond 6 weeks). An interim analysis of the primary endpoints will be performed on the soft-locked data for internal Myoscience purposes. The full dataset will be locked upon completion of all visit and adverse event follow-ups and this data will be reported in the clinical study report.

10.4.2 Secondary Effectiveness Endpoints

The secondary effectiveness endpoints are as follows:

1. AUC/time (see definition of AUC/time below) based on Changes from Baseline in KOOS JR. Scores through 6 weeks post-TKA
2. AUC/time based on Changes from Baseline through 6 weeks post-TKA in NRS for Pain
3. AUC/time based on Changes from Baseline through 6 weeks post-TKA in Timed Get Up and Go (TUG) test

Change in KOOS JR. scores from the Baseline visit to each post-baseline visit will be calculated for each subject as:

$$\text{Change in KOOS JR. score} = \text{Post-Baseline Visit KOOS JR. score} - \text{Baseline Visit KOOS JR. score},$$

such that a positive value indicates an increase in the KOOS JR. score, while a negative value indicates a decrease. The first and key secondary effectiveness endpoint, AUC/time based on Changes from Baseline in KOOS JR. scores through 6 weeks post-TKA, is the area under the curve (AUC) of Change in KOOS JR. scores from the Baseline visit through the 6-week visit divided by the number of days from TKA until the 6-week visit. AUC will be calculated using the trapezoidal rule and the changes in the KOOS JR. score at the following time points: Baseline (change=0), 72 hours, 2 weeks, and 6 weeks post-TKA.

The difference in mean AUC/time between the two treatment groups will be calculated as the mean Active AUC/time – the mean Standard of Care AUC/time, such that a positive difference indicates that the Active Treatment group had a larger mean AUC/time based on Change in KOOS JR. score than the Standard of Care Treatment group, while a negative value indicates the opposite. Because a positive Change in the KOOS JR. score is indicative of pain relief, a positive difference between treatment groups reflects a positive outcome for this endpoint.

Let $\mu_{2,\text{Active}}$ and $\mu_{2,\text{SOC}}$ denote the true mean AUC/time based on the Change from Baseline in KOOS JR. score from the Baseline visit through the six-week visit for the active and standard of care treatments, respectively. Then the null and alternative hypotheses for the test for non-inferiority for this endpoint are as follows:

$$H_0: \mu_{2,SOC} - \mu_{2,Active} \geq \delta$$

$$H_1: \mu_{2,SOC} - \mu_{2,Active} < \delta,$$

where the non-inferiority margin $\delta=14$.

The null hypothesis will be tested using a two-independent sample t-test. One of the secondary objectives of the study is to show that, over the 6-week post-TKA period, the Active Treatment group has similar levels of pain and functioning as compared to the Standard of Care Treatment group. This objective will be met if the t-test for non-inferiority is statistically significant using a one-sided $\alpha = 0.025$ level of statistical significance.

The fixed sequential testing procedure will be used for the comparison of the two treatments with respect to the first (and key) secondary effectiveness endpoint. Therefore, for this endpoint, the analysis comparing the two treatments will be formally conducted only if the analysis for the primary effectiveness endpoint yields a statistically significant result. For informational purposes, however, the results of the analysis (i.e., p-value) will be presented regardless of the results for the primary effectiveness endpoint.

Each secondary effectiveness endpoint will be summarized by treatment using descriptive statistics. For each treatment, the null hypothesis that the true mean AUC/time equals zero will be tested using a paired t-test. Ninety-five percent confidence intervals based on the t-distribution for the true mean AUC/time for each treatment and for the true difference in these means between treatments will be provided. In addition, for each secondary effectiveness endpoint, the initial result (e.g., KOOS JR. score at 6-weeks post-TKA), as well as the Change from Baseline value, will be summarized at each visit at which data for the endpoint are collected using descriptive statistics.

The database will be “soft-locked” after all 6 week data has been collected (all data monitored with the exception of data points collected beyond 6 weeks). An interim analysis of the secondary endpoints will be performed on the soft-locked data for internal Myoscience purposes. The full dataset will be locked upon completion of all visit and adverse event follow-ups and this data will be reported in the clinical study report.

[REDACTED]

[REDACTED]

[REDACTED]

[REDACTED]

10.4.4 Safety

Adverse events (AEs) will be coded using the Medical Dictionary for Regulatory Activities (MedDRA). Treatment-emergent AEs (TEAEs) are adverse events with onset after study treatment begins and that are not present at baseline or, if present at baseline, have worsened in severity. For AEs with missing start dates, the AE will be considered treatment-emergent unless there is additional information indicating that the AE started prior to study treatment. Only treatment emergent AEs will be summarized.

The number and percentage of subjects with at least one TEAE, at least one device-related TEAE, at least one serious TEAE, at least one serious adverse device effect, at least one unanticipated serious adverse device effect, at least one anticipated serious adverse device effect, and at least one TEAE leading to study withdrawal will be presented by treatment group. AEs that are definitely, probably, or possibly related to the device, or for which the relationship to the device is missing, will be considered device-related. TEAEs will be summarized at the subject level by MedDRA system organ class (SOC) and preferred term using frequencies and percentages. TEAEs will also be tabulated at the event level by severity and by relationship to the device for each treatment group.

10.5 Handling of Dropouts or Missing Data

Missing data for the primary effectiveness endpoint and the first secondary effectiveness endpoint will be imputed using multiple imputation methods. First, the relatively uncommon, non-monotone missing data will be imputed using the MCMC option of SAS® PROC MI. For example, for the primary effectiveness endpoint, the imputation model will include a term for treatment and the pill counts at visits 4, 5, and 6. Second, the monotone missing values will be imputed using the chained equation method by SAS® PROC MI option MONOTONE REG. For each subject within each imputed dataset, the value of the endpoint will then be determined. The imputed data sets will each be analyzed as specified in Sections 10.4.1 and 10.4.2, and the results will be summarized using PROC MIANALYZE.

10.6 Analysis Windows

All analyses will be based on nominal visits.

10.7 Sensitivity Analyses

Sensitivity analyses may be considered and will be described in the final Statistical Analysis Plan for the study. Nevertheless, the primary results will be used when evaluating overall Study Success.

10.8 Sample Size Determination

The required sample size was determined based on providing at least 80% power for the primary effectiveness endpoint using a one-sided, two-independent sample, Satterthwaite t-test to test for non-inferiority of iovera treatment to Standard of Care treatment, with a significance level of 0.025, assuming a 1:1 allocation to treatment, a true treatment effect ($\mu_{1,Active} - \mu_{1,SOC}$) of -12.0 mg, and true standard deviations of 16.9 mg and 26.0 mg, for the iovera and Standard of Care treatments, respectively. Based on these specifications, the required sample size is 57 subjects per treatment group, for a total of 114 subjects. To account for a small number of the subjects withdrawing early or not having data available for the analysis of the primary effectiveness endpoint, the required sample size was increased to 120 randomized subjects (approximately 60 Active Treatment subjects and 60 Standard of Care Treatment subjects).

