### **3.4 Determination of Sample Size**

The sample size was determined based on the primary effectiveness endpoint, the cumulative consumption of opioids from the time of hospital discharge to 6 weeks post-TKA Surgery. Opioid consumption will be converted to morphine equivalents, and subject consumption will be verified by pill count at follow-up visits. The cumulative morphine equivalent will be divided by the number of days to provide the Total Daily Morphine Equivalent (TME) for the subject. Let  $\mu_{1,Active}$  and  $\mu_{1,SOC}$  denote the true mean TMEs for the active and standard of care treatments, respectively. The required sample size was determined based on providing at least 80% power for the primary effectiveness endpoint using a one-sided, two-independent sample, Satterthwaite t-test to test for superiority of iovera treatment to Standard of Care treatment, with a significance level of 0.025, assuming a 1:1 allocation to treatment, a true treatment effect ( $\mu_{1,Active} - \mu_{1,SOC}$ ) of -12.0 mg, and true standard deviations of 18.2 mg and 26.0 mg, for the iovera and Standard of Care treatments, respectively. Based on these specifications, the required sample size is 57 subjects per treatment group, for a total of 114 subjects. To account for a small number of subjects withdrawing early or not having data available for the analysis of the primary effectiveness endpoint, the required sample size was increased to 120 randomized subjects (approximately 60 Active Treatment subjects and 60 Standard of Care Treatment subjects).

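### The protocol's 57 per arm does not follow from its own standard deviations, which need 54; the SAP keeps 57 with a different SD and does not list the change

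*Protocol*

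**What the plan says.** Protocol section 10.8 (Sample Size Determination) specifies a one-sided Satterthwaite t-test "with a significance level of 0.025, assuming a 1:1 allocation to treatment", aims at "providing at least 80% power for the primary effectiveness endpoint", and takes a true difference of -12.0 mg (iovera minus standard of care) with "true standard deviations of 16.9 mg and 26.0 mg, for the iovera and Standard of Care treatments". From these it derives 57 per group (114 in total), then rounds up to 120 randomized to cover early withdrawal and unavailable data. It describes the test as one "to test for non-inferiority of iovera treatment to Standard of Care treatment".

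SAP section 3.4 (Determination of Sample Size) repeats the calculation with the same difference, alpha, power and allocation, and the same 57, 114 and 120. Two things differ: it gives "true standard deviations of 18.2 mg and 26.0 mg, for the iovera and Standard of Care treatments", and the test is now one "to test for superiority of iovera treatment to Standard of Care treatment".

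The primary hypotheses are the same in both documents (protocol 10.4.1, SAP 8.1): the null is that mean daily morphine equivalent on iovera is at least that on standard of care, and the alternative is that it is lower. No margin is given. SAP section 3.5, on changes to the protocol-specified analyses, covers only how the t-tests are obtained from the multiply imputed data sets.

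**The concern.** Two different SDs cannot both be the basis of the same minimum sample size unless the difference between them is too small to matter. Here it is not. The iovera variance moves from 16.9² = 285.61 to 18.2² = 331.24, and the sum of the two variances rises by 1007.24 / 961.61 = 1.047. That is 4.7%, or between two and three subjects per arm at this size. At least one document therefore has a number that does not belong to its calculation.

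What is at stake is traceability. Section 10.8 is the protocol's quantitative justification for randomizing 120 people. As it stands, it gives a required size that its inputs do not produce, and it names a type of test that the protocol's own hypotheses contradict. A report that quoted it would carry both errors forward, and a reader comparing the two documents could not tell which variance assumption was planned.

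**Working it through.** **Inputs** (protocol 10.8 and SAP 3.4): difference d = 12.0 mg; one-sided alpha 0.025; power at least 80%; 1:1 allocation; standard-of-care SD s₂ = 26.0 mg. The iovera SD s₁ is 16.9 mg in the protocol and 18.2 mg in the SAP.

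**Formulas**, with n per arm:

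- Normal approximation: n = (1.960 + 0.842)² × (s₁² + s₂²) / d², where the squared term is 7.849 before rounding.
- Satterthwaite t-test: SE = √((s₁² + s₂²)/n); noncentrality = d/SE; df = (n − 1)(s₁² + s₂²)² / (s₁⁴ + s₂⁴). The approximate power is the probability that a noncentral t on this df exceeds the 0.975 quantile of the central t.
- The exact version integrates over the distribution of the sample variance ratio, because the estimated df varies from sample to sample.

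**Step 1: the SAP figure (18.2 / 26.0).** s₁² + s₂² = 331.24 + 676 = 1007.24. The normal approximation is 7.849 × 1007.24 / 144 = 54.9, so 55.

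| n per arm | SE | noncentrality | df | power, approximate | power, exact |
|---|---|---|---|---|---|
| 55 | 4.279 | 2.804 | 96.7 | 79.28% | 79.27% |
| 56 | 4.241 | 2.830 | 98.5 | 80.006% | 79.997% |
| 57 | 4.204 | 2.855 | 100.3 | 80.71% | 80.70% |

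By the exact method 57 is the minimum, so the SAP's 57 per arm reproduces.

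**Step 2: the protocol figure (16.9 / 26.0).** s₁² + s₂² = 285.61 + 676 = 961.61. The normal approximation is 7.849 × 961.61 / 144 = 52.4, so 53.

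| n per arm | SE | noncentrality | df | power, approximate | power, exact |
|---|---|---|---|---|---|
| 53 | 4.260 | 2.817 | 89.3 | 79.58% | 79.57% |
| 54 | 4.220 | 2.844 | 91.0 | 80.33% | 80.32% |
| 57 | 4.107 | 2.922 | 96.2 | 82.44% | 82.43% |

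The minimum is 54 per arm, 108 in total, by both the approximate and the exact method. A pooled-variance t-test also gives 54. The stated 57 is 3 per arm and 6 in total too many.

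**Step 3: simulation check**, 2,000,000 trials per setting. With SD 16.9: 79.6% at 53, 80.3% at 54, 82.4% at 57. With SD 18.2: 79.98% at 56, 80.7% at 57.

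**Step 4: could another reading of the protocol give 57 at SD 16.9?** One-sided alpha 0.05 gives 43; alpha 0.0125 gives 65; 85% power gives 62; 90% power gives 72. A 57 appears with about 82% power, or with a difference near 11.7 mg, but the text states neither. It also appears as 54 / 0.95 = 56.8. That would be an attrition allowance, but the protocol gives 57 before attrition and then adds attrition separately (114 / 0.95 = 120).

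**Step 5: the type of test.** A non-inferiority calculation needs a margin. The only margin in either document is 14 points on KOOS JR., for the key secondary endpoint. With no margin, the calculation in 10.8 is a superiority calculation whatever it is called, so the word does not affect n.

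**The case against.** The strongest reply is that nothing in the trial depends on this. The discrepancy is conservative: 57 per arm meets the power target under either SD (82.4% or 80.7%), and 60 per arm gives 84.3% or 82.7%. The SAP's own section is internally consistent, and the primary hypotheses were always superiority, so the non-inferiority wording is a slip. All of that is right, and it limits the point to one of documentation. It does not make the protocol's figure follow from its inputs.

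Three narrower objections stand in part.

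- The match at 18.2 mg is on a knife edge. The common noncentral-t approximation gives 80.006% at 56 and so returns 56. By the exact method any iovera SD from 18.2 to 18.7 mg (in steps of 0.1) returns 57. Of the two stated SDs only 18.2 reproduces 57, but this is weak evidence about which one was planned. The 54 at SD 16.9 does not depend on the choice of method.
- The simplest explanation is that 57 was computed from 18.2 and that 16.9 is a misprint or a leftover. It need not mean that an assumption changed and n was not recomputed. This is plausible, but neither document gives a source for either SD, so it remains an inference.
- SAP 3.5 concerns changes to analyses, and a planning SD is arguably not an analysis. The opening pages of the SAP were also not in the available text, so a revision note there cannot be excluded. What can be said is that section 3.5 and the remaining text do not mention either difference.

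**Conclusion.** The concern holds: protocol 10.8 is wrong as written. Its stated inputs require 54 per arm (108 in total), not 57 (114). The SAP reaches the same 57 only by using a different iovera SD, 18.2 instead of 16.9 mg, without remark in section 3.5. The protocol's description of the calculation as non-inferiority contradicts its own primary hypotheses.

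The numerical error is 3 subjects per arm, or about 2.4 percentage points of power above the stated 80%. It errs on the safe side, so power is adequate and the enrolment target is unaffected. The result assumes normally distributed outcomes with the stated true SDs, as the plan's own t-test calculation does, and takes 57 as the size before attrition, as both documents state.

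**What to change.** Establish which iovera SD was used and cite its source, then make the two documents agree.

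- If it was 18.2 mg, correct the SD in protocol 10.8; 57 per arm stands. Name the power method, since the result at 18.2 depends on it.
- If it was 16.9 mg, restate the requirement in protocol 10.8 as 54 per arm, or keep 57 and state the power as 82.4%, and correct the SD in SAP 3.4.

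In either case, replace non-inferiority with superiority in protocol 10.8 and record both corrections in SAP 3.5. If the protocol can no longer be amended, the same statement in the SAP and the study report would give readers what they need. The cost is one or two figures, one word and a line in the list of changes. Enrolment, endpoint, test and alpha stay as they are.
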